8.4.4.4. Pre-MRI scan testing

Pregnancy Testing

Administer a pregnancy test (per institutional standard) to all female subjects of childbearing potential. The pregnancy testing may be done up to 7 days before the MRI scan. Document the results of the test. If the subject is pregnant, do not proceed any further. The subject should be withdrawn.

Clearing the Subject for the Study Scan

To safely perform an MRI scan on a subject with the implanted study system, the physician/clinician should do the following as stated in the MRI Procedure Information for the St. Jude Medical® MR Conditional defibrillation system:

- Confirm that the patient has an MR Conditional System
- Confirm that no adverse conditions to MRI scanning are present (e.g. additional hardware)
- Review the potential adverse events
- Generate a report of the patient's permanently programmed parameters
- Select and Save MRI Settings
- Review the MRI Checklist and Program the MRI Settings using the Merlin® PCS
- Subject receives the MRI Scan
- Disable MRI Settings Using the Merlin® PCS

The radiologist or staff, a designated radiological member, must determine the subject's eligibility for an MRI scan prior to the MRI scan (per standard of practice). However, the ICD/ CRT-D and lead (wires) contraindication item on the MRI hazard checklist do not apply if the subject is implanted with any one of the four main device systems included in this study.

The study MRI Hazard Checklist may be used to document a radiologist or designated member of the radiology department has cleared the subject for an MRI scan.

Alternatively, the radiology department may use its own hazard checklist in lieu of the study MRI Hazard Checklist. This documentation should be maintained with the subject's medical and/or study records.

Device Assessment and Programming

Interrogate the ICD/ CRT-D and obtain the following for the Study leads:

- In-clinic bipolar and unipolar* capture threshold at a pulse width of 0.5 ms. Either the manual decrement or automatic (in-clinic, programmer-based) method may be used to obtain the capture threshold.
Note: If the capture threshold is $> 2.5V$ at 0.5ms for RA and RV leads or $> 2.0V$ at 0.5 ms for LV leads, then the subject does not meet pre-MRI screening criteria.
- In-clinic bipolar sensing amplitude. Either the incremental or the automatic (in-clinic, programmer based) method may be used to obtain the sensing threshold.

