Note: If the ventricular sensing is not measurable (patient has underlying rhythm $< 30bpm$) and the sensing amplitude is $< 4mV$, then the patient does not meet pre-MRI screening criteria.
- In-clinic atrial and ventricular bipolar and unipolar* lead impedance

***NOTE:** *Unipolar and bipolar configurations should be collected for LV leads*

NOTE: *RV capture thresholds are not required to be obtained if a high ventricular rate is present (e.g. 110bpm). If available, sites should use the automatically obtained pacing capture threshold from the most recent archival data as a substitute for the in-clinic capture threshold. RV sensing measurements are not required if the subject's intrinsic rate has been established to be ≤ 30 beats per minute.*

If the device testing results do not meet the MRI conditions for scanning per the MRI Procedure manual (also see below), or the patient's sensing threshold is not measurable or the sensing threshold is less than 4mV, the physician may choose to reschedule the subject to return for re-testing. The subject's 1 Month Post MRI Scan Visit will need to be rescheduled to correspond with the MRI Scan Visit where the MRI scan was completed.

Review the MRI checklist on the programmer. Verify the following conditions before saving the MRI Setting.

- Bipolar capture thresholds are stable at $\leq 2.5V$ @ 0.5 ms for RA and RV leads or $> 2.0V$ @ 0.5ms for LV leads.
- Bipolar pacing lead impedance is within range, i.e. ≥ 200 and ≤ 2000 ohms
- HVLI is within range, i.e. ≥ 20 and ≤ 200 ohms
- No additional hardware (adaptors, extenders, or abandoned leads)

Save the MRI Setting after the MRI Checklist has been reviewed, using the parameters listed in **Table 5** for ICDs and **Table 6** for CRT-Ds. Perform all other applicable tests and procedures.

TABLE 5: MRI PARAMETERS-ICD

Parameters	Selectable Options	Nominal Values
MRI Mode*	VOO Pacing Off	Pacing off
MRI Base Rate	30-100 bpm, in steps of 5 bpm	n/a

Parameters	Selectable Options	Nominal Values
MRI RV Pulse Configuration	Bipolar	n/a
MRI RV Pulse Amplitude	5.0 V, 7.5 V	n/a
MRI RV Pulse Width	1.0 msec	n/a
Tachy settings	Disabled	Disabled

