8.4.4.5. MRI Scan procedures

Monitor subject with ECG and/or pulse oximetry and verbal communication.

Setting up Pulse Oximetry and/or ECG

Set up pulse oximetry and/or an ECG per standard of care. Place the oximetry clip on the subject's finger or other any other appendage that results in valid pulse oximetry readings. Or, position MRI compatible surface electrodes on the subject to ensure the subject's heart rate can be continuously monitored during the scan. During the MRI scan, periodically record heart rate, and blood oxygen saturation levels. Visually examine the ECG during the MRI scan. After the MRI scan, remove the subject from the MRI field.

MRI Scan

After confirmation by the electrophysiologist or device specialist that all pre-MRI system checks (mentioned above) have been met, subjects will have their MRI scan completed by a radiology staff member. **Note:** If the subject does not pass the Pre-MRI scan System Check specified above, then the subject should not undergo an MRI scan. The subject can be rescheduled to come back to repeat the Pre-MRI scan System Check testing within the visit window.

Protocol required MRI scan sequences for each subject undergoing an MRI scan are described in detail in the MRI Scan Guidelines. It is recommended that the MRI scan be set up on the MRI scanner in advance of the first subject scheduled for a study scan to ensure the scan has been appropriately programmed and to provide adequate time to address any questions or issues that may arise.

Subjects will undergo two different scans for the study, both of which will expose the ICD/ CRT-D to extreme scanning conditions: (1) a thoracic scan that is RF intensive, and (2) a head scan that is gradient intensive. The thoracic scan should be set up to last about 6 minutes and 15 seconds, and the head scan should be set to get as close as possible to 5 minutes without being under 5 minutes. The thoracic scan will need to be repeated 4 times to ensure the subject is scanned approximately 25 minutes. Further details about the set-up, programming and ways to adjust the parameters for MRI scans can be found in the MRI Scan Guidelines.

The subject may be in the bore or near the vicinity of the magnet for approximately 60 minutes. The actual amount of time the subject will be scanned is about 30 minutes: 25 minutes for the thoracic scan, and 5 minutes for the head scan.

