8.4.4.6. Post MRI scan testing

Device Assessment and Programming

Following the MRI Scan, remove the subject from the MRI bore. Interrogate the ICD/CRT-D. Disable the MRI Settings. **Note: MRI settings must be disabled to ensure that tachyarrhythmia therapy is turned back on.** Obtain the following for the study leads: Interrogate the ICD/ CRT-D, and obtain the following for the Study leads:

- In-clinic bipolar and unipolar* capture threshold at a pulse width of 0.5 ms. Either the manual decrement or automatic (in-clinic, programmer-based) method may be used to obtain the capture threshold.
- In-clinic bipolar sensing amplitude. Either the incremental or the automatic (in-clinic, programmer based) method may be used to obtain the sensing threshold.
- In-clinic atrial and ventricular bipolar and unipolar* lead impedance

**NOTE: Unipolar and bipolar configurations should be collected for LV leads*

***NOTE:** RV capture thresholds are not required to be obtained if a high ventricular rate is present. If available, sites should use the automatically obtained pacing capture threshold from the most recent archival data as a substitute for the in-clinic capture threshold. RV sensing measurements are not required if the subject's intrinsic rate is established to be ≤ 30 beats per minute.*

Reporting of MRI Scan-Related Adverse Events

An ADE or SADE related to the following should be reported as soon as possible, but no later than 24 hours after the site becomes aware of the event, to Abbott: clotting, pulmonary embolism, or heating of the device pocket during the MRI scan. These events are likely to be associated with symptoms occurring during or immediately following the MRI scan and may manifest as chest pain, shortness of breath, or changes in vital signs during or immediately following the MRI scan.

To ensure all ADEs or SADEs related to or caused by the MRI scan are appropriately captured, before starting the scan, verbally instruct the subject to report symptoms of chest

pain, shortness of breath or pocket discomfort that he/she experiences while being scanned or immediately after exiting the scanner. Note changes in vital signs such as changes in heart rate, room air blood oxygen saturation, and/or respiration rate that occur during the MRI scan that may suggest an ADE or SADE has occurred due to clotting, pulmonary embolus or related to lead tip or device pocket heating.

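### Section 8.4.4.4: the ventricular sensing screen-out note joins its two conditions with *and*, so read literally it never fails a measured amplitude below 4 mV

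*Combined protocol and SAP*

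**What the plan says.** The sensing rule is spread over several places in the protocol.

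- **Screen-out note (8.4.4.4).** The subject fails pre-MRI screening under this condition: "If the ventricular sensing is not measurable (patient has underlying rhythm $< 30bpm$) and the sensing amplitude is $< 4mV". No other sentence in the protocol attaches a screening failure to the 4 mV figure.
- **Re-testing paragraph (8.4.4.4).** It covers device results that miss the MRI conditions for scanning and then adds two sensing grounds joined by *or*: "sensing threshold is not measurable or the sensing threshold is less than 4mV, the physician may choose to reschedule the subject" for another test.
- **Pre-save list (8.4.4.4).** Under the instruction "Verify the following conditions before saving the MRI Setting" it gives four items: capture threshold, pacing impedance, high-voltage lead impedance and additional hardware. None concerns sensing.
- **Measurement waiver (8.4.4.4).** "RV sensing measurements are not required if the subject's intrinsic rate has been established to be" 30 beats per minute or less. Sections 8.4.4.6 and 8.4.4.7.1 repeat it.
- **Scan gate (8.4.4.5).** An electrophysiologist or device specialist must first confirm that all the pre-scan checks described earlier were met. Then: "If the subject does not pass the Pre-MRI scan System Check specified above, then the subject should not undergo an MRI scan". A repeat is provided for: "The subject can be rescheduled to come back to repeat the Pre-MRI scan System Check testing within the visit window".

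The notes to Tables 5 and 6 add that the device does not sense while the MRI Settings are on, and that asynchronous pacing is available for subjects who need support.

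**The concern.** An eligibility limit should fail the subjects on the wrong side of it. This note combines two conditions that can hardly be observed together: no usable ventricular signal, and a value for that signal below 4 mV. The subject whom a 4 mV limit would naturally catch, one with a low but recorded amplitude, does not satisfy the first condition.

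The rule decides who may undergo an investigational scan, in a study with at least 6 centers. The scan gate in section 8.4.4.5 depends on which results count as not passing the check, and the only sentence that declares a sensing failure is worded so that a low measured value is not one. Section 17.1 grants no waivers and requires every deviation to be reported. On the note alone, a monitor could not say whether scanning a subject measured at 2 mV is a deviation.

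**Working it through.** The documents give no figure to reproduce here. SAP section 2.4 states that no sample size or power calculation was done, and no alpha, power or success criterion depends on this rule. The check is one of logic: take each sensing state and apply each rule as written.

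**Step 1. The note.** Fail = (not measurable) AND (amplitude below 4 mV).

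- Measured at 4 mV or more: false AND false, so not failed.
- Measured below 4 mV: false AND true, so not failed.
- Not measurable: true AND undefined. The subject fails only if an absent signal is counted as below 4 mV.

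**Step 2. The other rules, side by side.**

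| Sensing state | Screen-out note | Re-testing paragraph | Pre-save list |
|---|---|---|---|
| Measured, 4 mV or more | not failed | not named | silent |
| Measured, below 4 mV | not failed | named | silent |
| Not measurable | failed only if no signal counts as below 4 mV | named | silent |

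The note fails 0 of 3 states, or 1 of 3, depending on how an absent signal is classed. The re-testing paragraph names 2 of 3 either way.

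**Step 3. What the 4 mV figure does in the note.** If an absent signal counts as below 4 mV, every subject meeting the first condition meets the second, and the figure changes nothing. If it does not count, the note is never met. On both readings the cut-off separates no subject from any other.

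**Step 4. Intent.** The re-testing paragraph puts a value below 4 mV in the same sentence as results that miss the MRI conditions for scanning, under the same verb. Subjects in that latter group may not be scanned. The optional element is therefore best read as the re-test, not the scan. The confirmation step in section 8.4.4.5 points the same way.

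**Step 5. Would replacing *and* with *or* be enough?** With *or*, both the measured-below-4 mV state and the not-measurable state would fail. The second result sits badly with the waiver, which excuses the RV sensing measurement at an intrinsic rate of 30 bpm or less, and with the asynchronous pacing options. The two states need separate rules.

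**Step 6. Rate cut-off.** The note uses below 30 bpm; the waiver uses 30 bpm or less in three places. They differ only at exactly 30 bpm.

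**The case against.** The strongest reply is that this is a drafting slip which no qualified reader would follow. The literal reading leaves the 4 mV figure idle, the *or* version appears shortly afterwards in the same section, and the specialist must confirm that the pre-scan checks were met before the subject is scanned. A specialist would hardly give that confirmation for a result the protocol has just named as a ground for re-testing. Most of this stands, and it is why the point is limited to wording.

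Several stronger readings are tempting, but the documents do not support them:

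- **That the protocol leaves the scan optional below 4 mV.** The permissive verb also governs results that miss the MRI conditions, which section 8.4.4.5 says must not be scanned. It cannot fairly be read as permission to scan.
- **That centers will apply different rules.** This is possible, but nothing in the documents shows it.
- **That the capture-threshold note proves the error by contrast.** Its condition is "If the capture threshold is $> 2.5V$ at 0.5ms for RA and RV leads or $> 2.0V$ at 0.5 ms for LV leads". That *or* joins limits for different leads, so it says little about how two conditions on one signal should combine.
- **That the pre-save list wrongly omits sensing.** The list may simply repeat the conditions of the MRI Procedure manual, with sensing as a separate study criterion stated earlier.

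The reply does not remove the point. The sentence that declares the failure still says something other than what was meant, and the intended rule must be inferred from a paragraph about rescheduling. Nor does inference settle the not-measurable case at low intrinsic rates: the waiver and pacing provisions lean towards allowing the scan, the re-testing paragraph against.

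**Conclusion.** The note is wrong as written and should be corrected. Read literally, it never fails a subject with a measured ventricular amplitude below 4 mV. The surrounding text makes it fairly clear that such a subject was meant to be held.

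The size is modest. The number of subjects with sensing below 4 mV or not measurable is not given, and none is assumed. A reader might infer a patient-safety hazard, but the documents establish no specific scan risk from low sensing, and sensing is off during the scan in any case. The study is descriptive (SAP sections 2.2 and 2.7), so no hypothesis test or statistical success criterion is affected.

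The conclusion rests on the protocol text alone. The MRI Procedure manual and the MRI Screening Form are not among the documents and may already state the rule correctly. If so, the protocol still needs to agree with them.

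**What to change.** 1. Reword the note along these lines: *A subject whose measured ventricular sensing amplitude is below 4 mV fails pre-MRI screening and should not be scanned; re-testing is allowed within the visit window.*
2. Make the re-testing paragraph match: the re-test is optional, and scanning at that result is not allowed.
3. Add one sentence saying whether a subject whose sensing is not measurable because the intrinsic rate is 30 bpm or less may be scanned. Which way to decide is a clinical matter for the sponsor.
4. Check that the MRI Procedure manual and the MRI Screening Form say the same.

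Adding sensing to the pre-save list as a fifth item, and using 30 bpm or less throughout, are optional tidying.

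The cost is a wording amendment and site retraining, and possibly a few subjects who are re-tested or not scanned. No new type of procedure, additional enrollment or further data item is needed, since section 8.4.4.5 already provides for re-testing within the window.

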- **Group 4** will have at least 15 enrolled subjects with a Quadra Assura MP CRT-D and an Optisure or Durata lead in the RV, an Isoflex or Tendril STS lead in the RA, and a Quartet lead in the LV.

The enrollment group and group 4 lead pairing will be at the discretion of the Investigator, dependent on patient needs in conjunction with study needs to fulfill study goals.

At least forty-five (45) days after system implantation or after a system revision, subjects will have a baseline visit followed by an MRI visit; subjects will undergo a study-related MRI scan at 1.5T. Subjects will have a 1-month follow-up after the study MRI scan. The minimum duration of each subject's participation is approximately 2.5 months from enrollment. The expected duration of enrollment is approximately 14 months. The total duration of clinical study is expected to be 16.5 months.

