8.1.11. Anticipated participation duration of each subject

Each subject is anticipated to participate in this clinical investigation for 2.5 months from the time of enrollment. This accounts for the 45-day post-implant stabilization period and 30 days for completion of the 1-month post-MRI visit.

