8.2.1. Description of the effectiveness endpoints

- Proportion of leads with a capture threshold increase of $\leq 0.5V$ at 0.5ms for RA and RV leads and $\leq 1.0V$ at 0.5ms for LV leads from pre-MRI scan to 1-month post-MRI scan testing.
- Proportion leads with a sensing amplitude decrease of $\leq 50\%$ from pre-MRI scan testing to 1-month post-MRI scan.

8.2.2. Selection of method and time for evaluation, recording and analysis of the effectiveness endpoints

Since the objective is to evaluate the effect of MRI exposure for the ICD/ CRT-D device groups included in this study, the effectiveness parameters were selected to compare abnormal changes in device performance from pre- to 1-month post- MRI scan. The pre-MRI measurements are collected within the same day prior to the MRI scan. The 1-month post-MRI scan measurements are collected at 30 days post-MRI scan (within +14 days) to ensure any effect of the MRI exposure is captured.

The effectiveness parameters are recorded directly from the device. The device measurements will be obtained using the Merlin programmer to interrogate the device during study visits. The analysis of the effectiveness parameters will be conducted on all subjects with complete data from pre- to 1-month post-MRI scan.

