8.4.5. Situations where subject does not meet enrollment criteria

If a subject does not meet all inclusion criteria or meets any of the exclusion criteria, the subject cannot participate in the study and cannot be enrolled.

In case the subject was already consented to participate in the study, but did not meet inclusion/exclusion criteria, the following actions will be taken (**Table 7**). The EC/IRB should be notified of deviations according to each respective entity's guidelines.

TABLE 7: ACTIONS FOR INCLUSION/EXCLUSION CRITERIA ISSUES OCCURRING POST CONSENT

Issues where patient was consented, but did not meet inclusion/exclusion criteria	Action
If the subject did not have a successful implant procedure or successful re-attempt to implant with the study devices	
 • Document consenting information (name of the study, date of consent and inclusion/exclusion) in the subject's medical and/or study records • Complete the withdrawal CRF. The subject is withdrawn.
If the MRI Pre-Scan Visit has taken place, the MRI Settings was NOT programmed and the study MRI scan was NOT completed (e.g. Subject changed their mind about undergoing MRI scan, etc.)	
 • Document enrollment (name of the study, date of consent and inclusion/exclusion), MRI Scan Visit and study MRI scan information in the subject's medical and/or study records • Complete the Pre-MRI Scan Form • Note that the subject did not have the MRI Settings programmed on the pre-MRI CRF. • Complete deviation for inclusion/exclusion criteria not met • Complete the Withdrawal CRF. The patient is withdrawn.
If the MRI Pre-Scan Visit has taken place, the MRI Settings WERE programmed but the study MRI scan was NOT completed (e.g. Subject changed their mind about undergoing MRI scan, etc.)	
 • Document enrollment (name of the study, date of consent and inclusion/exclusion), MRI Scan Visit and study MRI scan information in the subject's medical and/or study records • Complete the Pre-MRI Scan Form • Complete deviation for inclusion/exclusion criteria not met • Complete the Withdrawal CRF. The patient is withdrawn.

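### Protocol Section 8.4.4.4 reverses the LV capture-threshold condition for scan clearance: above 2.0 V fails in one place and is required in the other (Group 4 only)

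*Combined protocol and SAP*

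**What the plan says.** Section 8.4.4.4 (Pre-MRI scan testing) sets the capture-threshold limits twice.

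- The note under capture testing is a fail rule. The limit is 2.5 V for RA and RV leads, and for LV leads it reads: "> 2.0V$ at 0.5 ms for LV leads, then the subject does not meet pre-MRI screening criteria".
- The later list, to be verified before the MRI Setting is saved, is a pass rule. It asks for stable bipolar thresholds at or below 2.5 V "for RA and RV leads or $> 2.0V$ @ 0.5ms for LV leads".

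Between the two, the paragraph on re-testing refers to the "MRI conditions for scanning per the MRI Procedure manual (also see below"), which appears to send the reader to that same list.

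Section 8.4.4.5 makes the check binding: "If the subject does not pass the Pre-MRI scan System Check specified above, then the subject should not undergo an MRI scan". Re-testing within the visit window is allowed. In Table 7 (Section 8.4.5), a subject for whom the "MRI Settings was NOT programmed and the study MRI scan was NOT completed" is withdrawn. Section 8.2.2 says the effectiveness analysis "will be conducted on all subjects with complete data from pre- to 1-month post-MRI scan".

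Section 8 says Group 4 "will have at least 15 enrolled subjects with a Quadra Assura MP CRT-D", and it is the only group with an LV lead. Section 8.1.12 explains that 15 are enrolled per group to secure the 10 that the NMPA asked for, with 5 allowed for attrition.

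**The concern.** The item decides who in Group 4 is scanned. A site working from the list alone would clear exactly the LV leads that the note excludes and block those that it accepts. Its Group 4 sample would be the complement of the intended one. A site applying both statements literally could clear nobody. Sites that settled the conflict differently would contribute differently selected subjects to the same group.

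Re-testing does not cure a wrong block: a good LV lead that stays at or below 2.0 V fails the list again. A subject who is never programmed and never scanned is withdrawn and supplies no pre-scan to 1-month data. Every Quartet lead observation in the study passes through this condition. In addition, on the literal reading, scanning any Group 4 subject breaches one of the two statements. Section 17.1 grants no waivers and requires all deviations to be reported.

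**Working it through.** The protocol gives no figure to reproduce here, so the check is a comparison of the two rules followed by a count of what they touch.

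**Comparison of the rules.** Let x be the capture threshold in volts at 0.5 ms.

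| Lead | Note (fail rule) | Note implies pass | List (pass rule) | Values passing both |
|---|---|---|---|---|
| RA, RV | x > 2.5 fails | x ≤ 2.5 | x ≤ 2.5 | x ≤ 2.5 |
| LV | x > 2.0 fails | x ≤ 2.0 | x > 2.0 | none |

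For example, an LV threshold of 1.0 V passes the note and fails the list; 2.5 V fails the note and passes the list.

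**Could another reading reconcile them?**

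- *Bipolar versus unipolar.* The list refers to bipolar thresholds, while LV leads are tested in both configurations. That does not explain requiring a high LV threshold.
- *The word or as a true alternative.* The note uses the same word to separate limits by lead position. If it were a real alternative in the list, an LV lead above 2.0 V would still get through whenever the right-sided leads passed, which the note forbids.
- *A misread symbol.* The text was taken from PDF. The ≤ sign in the same bullet was read correctly, so a misread LV sign is unlikely, though it cannot be excluded without the original.

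The likeliest explanation is that the fail rule was rewritten as a pass rule and only the RA/RV sign was changed.

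**Scope at minimum enrollment** (15 per group, Section 8; leads per subject from the group definitions in Section 2.1):

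- Subjects: Group 4 is 15/60 = 25%. Groups 1 to 3, with no LV lead, are 45/60 = 75%.
- Leads: 15×1 + 15×2 + 15×2 + 15×3 = 120. LV leads are 15/120 = 12.5%, all in Group 4.
- Literal limit: with no value passing both rules, 0 of 15 would be cleared. This is a logical bound, not a forecast.

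**Slack and replacement.** The attrition allowance is 15 − 10 = 5 subjects in Group 4. Beyond it, each replacement needs a new implant. Section 8.1.11 gives the time: "This accounts for the 45-day post-implant stabilization period and 30 days for completion of the 1-month post-MRI visit", so at least 45 + 30 = 75 days from implant to the 1-month visit.

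**After correction.** With the list at ≤ 2.0 V for LV leads, both statements pass x ≤ 2.0 and fail x > 2.0. The RA/RV rule already agrees.

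**The case against.** The strongest reply accepts the conflict and disputes its weight. Section 8.4.4.5 requires an electrophysiologist or device specialist to confirm that all the earlier checks are met, and the note is one of them, so a site relying on the list alone would not be following the protocol. The RA/RV half of the same bullet shows the intended direction, and a qualified reader would probably notice the slip. Clearance also runs through the programmer's checklist and the MRI Procedure manual, which may carry the right limit. Up to 5 Group 4 losses leave the minimum of 10 intact without replacement, and enrollment targets are minimums. There is no hypothesis test, success criterion or power calculation to disturb (SAP Sections 2.4 and 2.7).

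Much of this stands. It rules out treating 0 of 15 as an expected result, and the 75-day replacement cost arises only once the allowance of 5, shared with all other attrition, is used up. It does not remove the contradiction. The manual and the programmer checklist are not among the documents, so what they say cannot be relied on here, and the protocol's own reference to the manual appears to lead to the faulty list. A scan-clearance condition should not depend on the reader noticing that it is wrong.

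**Conclusion.** The concern holds. One eligibility threshold in a scan-clearance step is wrong as written, and nothing else in the documents reconciles it with the note. It affects Group 4 only: 15 of 60 subjects and 15 of 120 leads at minimum enrollment, but all of the LV lead data. Those figures show where the condition applies, not how many subjects would be misdirected. The documents do not give the share of subjects with LV thresholds at or below 2.0 V, so no expected number is offered.

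The conclusion assumes that the symbol was read correctly from the PDF and that the note, not the list, states the intended limit. No harm in the scanner is claimed, since Table 6 sets ventricular pacing during MRI to RV only. Nothing in the SAP changes. It should be fixed because it governs clearance for the investigational procedure and is cheap to correct.

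**What to change.** In the Section 8.4.4.4 list, change the LV condition to ≤ 2.0 V at 0.5 ms. Check the symbol in the original document, confirm the limit against the MRI Procedure manual, and correct any case report form or site checklist that repeats the reversed item.

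The cost is a short protocol amendment of one symbol. Section 17.2 requires ethics committee acknowledgement or approval in writing before it takes effect, at six or more centers (Section 4.3). No visit, procedure or analysis is added.
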